This is a placebo-controlled, randomized controlled trial to investigate the role of vaginal cryotherapy on pelvic floor myofascial pain in women. This study involves randomizing patients who are found to have pelvic floor myofascial pain on examination into one of two treatment groups: transvaginal cryotherapy or transvaginal application of a room-temperature tube. Patients will be followed up at two different time points in order to assess response to treatment. Follow-up times include immediately after application (Specific Aim #1) and two weeks following use of the intervention alone (Specific Aim #2). Patients will be referred to pelvic floor PT, which is considered the standard of care for treatment of pelvic floor myofascial pain at this time. As it typically takes 2-3 weeks to get in to see one of the pelvic floor PT providers at Wash U, follow up for this study will be completed prior to their attendance at pelvic floor PT.

E2 Subject Selection and Withdrawal

2.a Inclusion Criteria

Study population and eligibility: All new patients presenting to our facility undergo our standardized pelvic floor myofascial examination and are asked to rate their pain on palpation of the bilateral OI and LA muscles on a 0-10 verbal pain rating scale (0=none 1-3=mild, 4-6=moderate, and 7-10=severe). Patients found to have pelvic floor myofascial pain of at least 4/10 in severity at any of the four sites will be eligible for inclusion. Eligible patients may participate in Specific Aim 1 only or in both Specific Aims 1 and 2.

2.a Exclusion Criteria

Exclusion criteria include age <18, non-English speaking, current diagnosis of dementia, and limited physical mobility that would prevent full participation in pelvic floor PT. Patients will also be excluded if they have performed vaginal cryotherapy in the past or present with a complaint or known history of chronic pelvic pain.

2.b Ethical Considerations

Human Subjects Involvement and Characteristics

We will approach adult women presenting to the FPMRS Clinic at Washington University in St. Louis for inclusion. Eligible women will be ≥ 18 years old, English speaking, found to have pelvic floor myofascial pain on examination, and willing to participate.

Inclusion of Women, Minorities, and Children

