All new patients presenting to our facility undergo our standardized pelvic floor myofascial examination and are asked to rate their pain on palpation of the bilateral OI and LA muscles on a 0-10 verbal pain rating scale (0=none 1-3=mild, 4-6=moderate, and 7-10=severe). Patients found to have pelvic floor myofascial pain of at least 4/10 in severity at any of the four sites will be considered eligible and approached for study inclusion. Exclusion criteria include age <18, non-English speaking, current diagnosis of dementia, limited physical mobility that would prevent full participation in pelvic floor PT, complaint or known diagnosis of chronic pelvic pain or prior use of vaginal cryotherapy. We will enroll a total of 66 patients for the trial.

F2 Schedule of Measurements

Data collection will occur at baseline and 2 weeks (**Figure 2**). Patients will complete validated questionnaires including the short forms of the Pelvic Floor Distress Inventory (PFDI-20), Pelvic Floor Impact Questionnaire (PFIQ-7), and Pelvic Organ Prolapse/Urinary Incontinence Sexual Questionnaire IUGA-Revised (PISQ-IR, 24, 25). Questionnaires will be scored according to published protocols (26, 27). (see attached)

F3 Safety and Adverse Events

The risks of the proposed study primarily include discomfort and embarrassment with the pelvic examination. This risk is not unique to study participants as all new patients undergo a comprehensive pelvic floor myofascial examination. Participants may also experience discomfort or embarrassment with intravaginal tube placement. Finally, breach of confidentiality is another risk. Every precaution will be taken to ensure data are kept strictly confidential. Only the research team will have access to paper data, which will be stored in a locked cabinet in the FPMRS offices. Enrolled patients will be assigned unique study identification numbers. A password-protected electronic database will be established using REDCap, and only the research team will have access. No results will be presented in a personally identifiable manner.

3.a Safety and Compliance Monitoring

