Grade IV	Life-threatening complication (including CNS complications)* requiring IC/ICU management
Grade IVa	Single organ dysfunction (including dialysis)
Grade IVb	Multiorgan dysfunction
Grade V	Death of a patient
Suffix "d"	If the patient suffers from a complication at the time of discharge (see examples in Table 2), the suffix "d" (for "disability") is added to the respective grade of complication. This label indicates the need for a follow-up to fully evaluate the complication.

*Brain hemorrhage, ischemic stroke, subarachnoidal bleeding, but excluding transient ischemic attacks.
CNS, central nervous system; IC, intermediate care; ICU, intensive care unit.

F4 Study Outcome Measurements and Ascertainment

The data collected will include demographic characteristics; basic medical and reproductive health histories; pre- and post-treatment myofascial examination scores; PFDI-20, PFIQ-7, and PISQ-IR results at baseline and follow up visits; PGI-I and SAPS scores at study conclusion; PFPT assessments. Demographic data, medical and reproductive health histories, and pre- and post-treatment myofascial examination scores will be obtained from the medical record. Baseline questionnaires will be completed by the patient electronically directly in REDCap using a secure, password-protected tablet owned and operated by the research team. Follow up surveys and questionnaires will be administered electronically as secure surveys built in REDCap.

G Statistical Plan

G1 Sample Size Determination and Power

We expect vaginal cryotherapy to result in at least 3-point improvement in myofascial pain scores as reported on a 0-10 verbal pain rating scale. Prior studies investigating clinically significant reductions in pain scores report greater than 2 points on a 0-10 scale or 30% reduction in pain as clinically significant²⁸. In order to detect a 3-point difference with 80% power and alpha 0.05, we would need to enroll 30 patients per group. Accounting for a 20% loss-to-follow up rate, we plan to enroll 33 patients per group for a total of 66 patients. Patients may participate in Specific Aim #1 only, in Specific Aim #2 only, or both Specific Aims. If no patients participate in both Specific Aim #1 and Specific Aim #2, then 132 patients will be required overall.

G2 Interim Monitoring and Early Stopping

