This study is designed as a pilot study to test the efficacy and feasibility of vaginal cryotherapy for treatment of pelvic floor myofascial pain. As such, we do not have futility criteria for early stopping. We will monitor for adverse events and pause/stop enrollment for this as indicated above.

G3 Analysis Plan

Specific Aim #1: To determine the effect of vaginal cryotherapy as an immediate treatment modality for patients with pelvic floor myofascial pain. Primary outcome is change in pelvic floor myofascial pain scores at each site (bilateral OI and LA). The statistical significance of this change between arms will be evaluated by a Students t-test or Wilcoxon rank sum test as appropriate. Secondary outcomes include change in PFDI-20, PFIQ-7, and PISQ-IR scores.

Specific Aim #2: To determine the effect of vaginal cryotherapy as a neoadjuvant treatment modality for patients with pelvic floor myofascial pain awaiting pelvic floor PT. Primary outcome includes change in pelvic floor myofascial pain scores at each site (bilateral OI and LA) from baseline to follow-up (2 weeks). The statistical significance of this change between arms will be evaluated by a Students t-test or Wilcoxon rank sum test as appropriate. Secondary outcomes include change in PFDI-20, PFIQ-7, and PISQ-IR scores, and patient satisfaction (PGI-I, SAPS).

G4 Missing Outcome Data

Patients with missing outcome data for the primary outcome will be excluded from analysis. The primary analysis will be by intention-to-treat with a planned secondary analysis per-protocol. Missing outcome data for secondary outcomes of PFDI-20, PFIQ-7, and PISQ-IR scores will be imputed according to published protocols for imputation of missing data within these questionnaires (26, 27).

H Data Handling and Record Keeping

H1 Confidentiality and Security

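### Entry needs pain of 4/10 at one of four sites, but the primary outcome is change at every site, so each site's comparison is diluted by women with little or no pain there

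*Combined protocol and SAP*

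**What the plan says.** Eligibility is set per patient. E2 (2.a Inclusion Criteria) asks for "pain of at least 4/10 in severity at any of the four sites will be eligible for inclusion", and F1 repeats the rule: "at least 4/10 in severity at any of the four sites will be considered eligible and approached for study inclusion". Neither section sets a minimum at the remaining sites. The scale is a "0-10 verbal pain rating scale (0=none 1-3=mild, 4-6=moderate, and 7-10=severe").

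The primary outcome is set per site. For Aim 1, G3 states: "Primary outcome is change in pelvic floor myofascial pain scores at each site (bilateral OI and LA"). For Aim 2 it states: "Primary outcome includes change in pelvic floor myofascial pain scores at each site (bilateral OI and LA) from baseline to follow-up (2 weeks"). The arms are compared by t-test or Wilcoxon rank sum test. Under G4 the primary analysis is by intention-to-treat and drops only women whose primary outcome is missing.

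The sample size in G1 rests on a 3-point effect that is not tied to any site: "We expect vaginal cryotherapy to result in at least 3-point improvement in myofascial pain scores", and "In order to detect a 3-point difference with 80% power and alpha 0.05, we would need to enroll 30 patients per group". No standard deviation is given. No section names an index or worst site, defines a summary score, or limits a site's analysis to women with pain there.

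**The concern.** The entry threshold guarantees room to respond at one site per woman, whereas the primary analysis looks at four. A woman scoring 4 at one levator site and 0 elsewhere is eligible. She contributes to four primary comparisons in each aim and can improve in only one of them.

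At stake is how the primary result would be read. If cryotherapy takes 3 points off pain wherever there are 3 points to take, each site's mean difference will still fall short of 3, because some women at that site had nothing to lose. The per-site estimates would then understate the effect at painful muscles, and each test would have less power than G1 suggests.

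This differs from the number of tests and from baseline adjustment. A single site, tested alone and adjusted for baseline, would still include women with no room to improve there.

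**Working it through.** **Inputs from the plan.** Entry is at least 4/10 at any of four sites (E2, F1). The scale runs from 0 to 10 (E2). The planned effect is 3 points, with 80% power, alpha 0.05 and 30 per group (G1). About 57% of new patients have pain of at least 4/10 (I4). The per-site distribution, the between-site correlation and the SD are not given, so they are assumed below.

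**1. The plan's own figure.** The 30 per group cannot be reproduced without an SD, but it can be solved backwards (two-sided, normal approximation):

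SD = 3 × √(30/2) / (1.960 + 0.842) = 11.62 / 2.802 = 4.15.

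An SD of 3 would have needed only 16 per group, so if the true SD is near 3 the trial has slack.

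**2. The floor.** The largest possible fall is the baseline score itself. Baselines of 0, 1 and 2 allow at most 0, 1 and 2 points. A baseline of 3 still allows 3.

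**3. Simple dilution.** If a share q of women cannot improve at a site, the mean difference there is 3 × (1 − q). With 30 per group, power = Φ(difference / (SD × √(2/30)) − 1.960). At SD 4.15 the standard error is 4.147 × 0.2582 = 1.071; at SD 3 it is 0.775.

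| q (assumed) | Mean difference | Power, SD 4.15 | Power, SD 3 |
|---|---|---|---|
| 0 | 3.00 | 80% | 97% |
| 10% | 2.70 | 71% | 94% |
| 25% | 2.25 | 56% | 83% |
| 50% | 1.50 | 29% | 49% |

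Example: 2.25 / 1.071 − 1.960 = 0.14, and Φ(0.14) = 0.56.

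These figures overstate the loss in two ways. Women scoring 1 or 2 can improve a little, and women fixed at 0 also shrink the SD. When their change is set to 0 in a simulation, power at q = 25% and 50% is 64% and 45% for SD 4.15, and 89% and 69% for SD 3.

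**4. Plausible values of q.** Four equally correlated site scores were simulated (400,000 women, rounded and clipped to 0–10), with the mean set so that 57% have at least one site at 4 or more. The latent SD ran from 2.5 to 3.5. Among eligible women:

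| Correlation (assumed) | Site scores below 4 | Site scores below 3 | Mean of min(baseline, 3) per site |
|---|---|---|---|
| 0.4 | 54% | 39–44% | 2.0–2.2 |
| 0.6 | 45% | 29–33% | 2.3–2.5 |
| 0.8 | 32% | 15–20% | 2.7–2.8 |

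At a correlation of 0.9 the per-site mean is about 2.9, so dilution nearly vanishes. For mean differences of 2.0 to 2.8, power with 30 per group is 46–74% at SD 4.15, 73–95% at SD 3 and 87–99% at SD 2.5.

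**5. The worst baseline site.** Every eligible woman scores at least 4 there, so without measurement error min(baseline, 3) is 3.0. With error this no longer holds, because a woman at 4 is also close to the floor. With follow-up error of SD 3 (assumed, half shared between sites), a true 3-point effect shows as about 2.5 at the worst site and 1.9–2.3 per site. Across the error assumptions tried, the ranges were about 2.0–2.75 at the worst site and 1.3–2.4 per site. The worst site had at least as much power as a single site in every scenario. In the noisiest, power rose from about 50–69% to about 92%.

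**The case against.** The strongest reply is that nothing here is invalid. Sites with a baseline of zero are equally likely in both arms, so the mismatch does not inflate type I error and any distortion runs toward no effect. One tube acts on the whole region, so the average effect at each muscle in all randomised women is a legitimate question, and it also captures worsening at sites that were quiet at baseline. That stands: the cost is sensitivity and interpretation, not validity.

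Four stronger readings are tempting, and the documents do not support them.

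- A reader might infer that the per-site analysis contradicts the objective, which concerns women with moderate-to-severe pain. The objective defines the population per woman, and the any-site rule matches it.
- A reader might infer that a 3-point mean difference is impossible. In the simulation the mean baseline per site is 3.2 to 4.6, and G1 expects at least 3 points, so larger falls in some women could offset the floor in others. Capping every fall at 3 builds in part of the shortfall.
- A reader might infer that an effective treatment would be declared ineffective. Serious loss of power needs both a large SD and a wide spread between sites, and the plan documents neither. Most of the range of 2.0–2.8 exceeds the 2-point benchmark that G1 cites for clinical significance; only its lower end does not.
- A reader might infer that the worst site recovers exactly 3 points. It does so only without measurement error.

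The index site is also not the only workable choice. With follow-up error of SD 3, power was 87–94% per site, 95–97% at the worst site and 99–100% for the four-site mean. A pre-set mean would therefore serve for power, although it stays diluted and would need its own effect size.

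**Conclusion.** The mismatch is in the text and nothing elsewhere in the plan repairs it. The threshold applies to one site, the primary outcome to four, and women scoring 0–2 at a site enter a comparison in which they cannot improve by the assumed 3 points. The effect at each site is diluted toward zero.

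The size cannot be fixed from the documents. It runs from negligible (sites highly correlated, or an SD well below 4.15) to material (correlation near 0.4 with an SD near 4.15, where power at a site is about 46%, holding the SD fixed). The figures rest on equally correlated, normal-based site scores calibrated to the 57% in I4, on 57% being the share with any site at 4 or more, and on a 3-point fall wherever the scale allows it. G3 should be changed because the repair is cheap and improves the analysis; the evidence does not justify calling the design unsound.

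**What to change.** In G3, for both aims, replace the four per-site primary outcomes with one patient-level score: change at the index site, defined as the site with the highest baseline score, with ties broken by a pre-set site order. Eligibility makes this at least 4 in every woman. Report as secondary the change at each of the four sites, both in all women and in those with a baseline of at least 4 at that site, together with the four-site mean. In G1, state that the 3-point assumption refers to the index site, and give the SD assumed for it.

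The cost is wording, settled before results are seen. All four sites are already scored, so no extra data or patients are needed and no woman is dropped. The downside is more regression to the mean within each arm, because the site is chosen for its high baseline. It is expected equally in both arms, so the between-arm comparison is protected, but the plan should say that within-arm change is not to be read as a treatment effect.

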The risks of the proposed study primarily include discomfort and embarrassment with the pelvic examination. This risk is not unique to study participants as all new patients undergo a comprehensive pelvic floor myofascial examination. Participants may also experience discomfort or embarrassment with intravaginal tube placement. Finally, breach of confidentiality is another risk. Every precaution will be taken to ensure data are kept strictly confidential. Only the research team will have access to paper data, which will be stored in a locked cabinet in the FPMRS offices. Enrolled patients will be assigned unique study identification numbers. A password-protected electronic database will be established using REDCap, and only the research team will have access. No results will be presented in a personally identifiable manner.

2.f Early Withdrawal of Subjects

i When and How to Withdraw Subjects

Patients may request withdrawal from the study at any point. Patients who desire to withdraw from the study will need to inform the research assistant or PI via telephone or

in writing using the contact information in the consent document. Patients who elect to withdraw from the study will not be contacted about future study-related tasks.

ii Data Collection and Follow-up for Withdrawn Subjects

Data collection will stop when the patient requests withdrawal from the study. It is possible, depending on the timing of study withdrawal, that some data collection will have already occurred. This data will be used according to the protocol for data use in the study, however, no further data collection will occur. In the event that a patient withdraws and requests that her previously-collected data be destroyed and not included in the study outcomes, that will be done according to her wish.

E3 Study Intervention

3.a Description

The intervention group will be provided with one vaginal cryotherapy tube, filled with a mixture of isopropyl alcohol (2ml) and water (8ml) that has been kept in the freezer. This mixture results in a “slushy” consistency and prevents the solution from freezing solid thus decreases the risk of discomfort or injury due to the temperature of the tube. They will be instructed to store these tubes in their home freezer.

The control group will be provided with an identical tube that is empty. An empty tube was chosen as the control because a tube with room-temperature liquid may still be perceived as cold.

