The appropriate tubes will be distributed by the research assistant with instructions provided for their appropriate use. Patients participating in Specific Aim #2 will be given tubes to take home with instructions to keep the tubes in the freezer or at room temperature according to their treatment assignment. The research assistant will not be blinded to the treatment allocation in order that she may answer any questions related to the intervention.

Patients will self-administer the intervention in the office (Specific Aim #1) or at home (Specific Aim #2) while resting in a supine position for 10 minutes. A lubricant may be used for comfort with tube insertion.

3.e Subject Compliance Monitoring

Patients will be asked to complete a short diary for each session, which will include the time of day, duration of application, pain score prior to and after application, and presence of any pelvic floor symptoms prior to and after application. This survey will be completed electronically via REDCap. The link will be sent via a secure email to the patient at the email address provided at the time of enrollment.

3.f Prior and Concomitant Therapy

There will be no requirement for prior therapy in order to participate in the study. Patients will be excluded from participation if they have previously used vaginal cryotherapy. All participating patients will be referred to pelvic floor physical therapy. There is frequently a delay in scheduling pelvic floor physical therapy of up to 2-3 weeks after initial referral thus this time was built into the study procedures in order to assess for the effect of cryotherapy independent of physical therapy. The 2 week follow up visit will occur concurrently or just prior to their first pelvic floor physical therapy visit.

3.g Blinding of Study Drug

The tubes are identical in appearance with the exception of the temperature to touch and contents. The tubes will be distributed to the patients by the research assistant, who is not blinded to treatment allocation. The patients will not be blinded to treatment allocation. The providers, who are blinded to treatment allocation, will not have contact with the tubes once distributed to the patient.

F Study Procedures

F1 Screening for Eligibility

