Vaginal cryotherapy is recommended routinely by the physicians and physical therapists in our Division and, to date, no adverse events related to the cryotherapy have been reported. Theoretical adverse events that could be related to use of cryotherapy in the vagina include skin irritation or injury from the temperature of the tube or trauma to the vagina related to placement of the tube.

Patients will be provided with contact information for study personnel who can be reached 24/7 to report an adverse event. At the follow up visit at 2 weeks, patients will be asked whether they experienced any adverse events. Follow up questions will be asked, as appropriate, for patients reporting adverse events during the study period. Adverse events will be monitored and recorded in the REDCap database. Adverse event reporting will occur throughout the duration of the study procedure.

Each reported adverse event will be reviewed by the members of the study team and graded according to the Dindo-Clavien classification for adverse events (see table). (32). Although this classification system is designed for surgical interventions, it is the most applicable classification system currently available for the intervention proposed in this

study. Any Class II or higher complications that are related or possibly related to the study intervention will result in a temporary cessation of enrollment and an investigation by the study team. A determination as to whether the study may resume will be made by the consensus of the study team. If more than 10% of enrolled patients report Class I complications that are related or possibly related to the study intervention, a similar process will occur.

TABLE 1. Classification of Surgical Complications

Grade	Definition
Grade I	Any deviation from the normal postoperative course without the need for pharmacological treatment or surgical, endoscopic, and radiological interventions Allowed therapeutic regimens are: drugs as antiemetics, antipyretics, analgesics, diuretics, electrolytes, and physiotherapy. This grade also includes wound infections opened at the bedside
Grade II	Requiring pharmacological treatment with drugs other than such allowed for grade I complications Blood transfusions and total parenteral nutrition are also included
Grade III	Requiring surgical, endoscopic or radiological intervention
Grade IIIa	Intervention not under general anesthesia
Grade IIIb	Intervention under general anesthesia

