In order to ensure the confidentiality of study participants, recruitment and consent will occur in a private examination or consult room. Patients will have ample time to ask questions of the study personnel. Patients will be determined to be eligible based on examination findings at the time of their initial evaluation. Medical record review will occur to confirm eligibility. Study-related activities will occur in a private examination room. Only the research team will have access to paper data, which will be stored in a locked cabinet in the FPMRS offices. Enrolled patients will be assigned unique study identification numbers. A password-protected electronic database will be established using REDCap, and only the research team will have access. No results will be presented in a personally identifiable manner

H2 Case Report Forms and Source Documents

All data will be securely stored in REDCap. Consent documents and hard copy documents will be securely stored in a locked cabinet in the FPMRS offices.

H3 Records Retention

Records of participating patients will be maintained throughout the study and data analysis. Records will be securely destroyed at the earliest possible time after completion of the study. Patients requesting withdrawl from the study and requesting any previously-captured results/data also be destroyed will have this information securely destroyed at the time of receipt of the request.

I Study Administration

I1 Organization and Participating Centers

The Female Pelvic Medicine & Reconstructive Surgery Division at Washington University in St. Louis is organizing and conducting this study. There are no other participating centers.

I2 Funding Source and Conflicts of Interest

This study is being funded by the Female Pelvic Medicine & Reconstructive Surgery Division at Washington University in St. Louis. All study personnel are without conflicts of interest.

I3 Subject Stipends or Payments

Study subjects will not be paid for their participation in this study.

I4 Study Timetable

Participation in this still will occur over 2 weeks. On average, we see about 30 new patients per month. Analysis from our cross-sectional data suggests that pelvic floor myofascial pain of at least 4/10 in severity is present in about 57% of new patients, thus we anticipate enrollment to take approximately 4-8 months, depending on the number of patients who choose to participate in both Specific Aims.

J Publication Plan

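### A woman who withdraws because of tube discomfort or injury is never actively asked about adverse events, so the safety record and the pause rules can miss her event

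*Combined protocol and SAP*

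**What the plan says.** Section E2 2.f lets a patient leave at any time by telephoning or writing to the research assistant or the PI. After that, "Patients who elect to withdraw from the study will not be contacted about future study-related tasks", and "Data collection will stop when the patient requests withdrawal from the study". Data already held are kept by default: "This data will be used according to the protocol for data use in the study, however, no further data collection will occur". They are removed only if the patient separately "requests that her previously-collected data be destroyed and not included in the study outcomes, that will be done according to her wish". H3 repeats that patients who make this request "will have this information securely destroyed at the time of receipt of the request".

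For safety, F3 3.a schedules one active question: "At the follow up visit at 2 weeks, patients will be asked whether they experienced any adverse events". It also provides a route that the patient must start herself: "Patients will be provided with contact information for study personnel who can be reached 24/7 to report an adverse event". Reporting is said to run throughout the study procedure. Reported events are graded. Any Class II or higher event that is at least possibly related pauses enrolment for a review. So does a share above 10% of enrolled patients reporting Class I events that are at least possibly related.

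The diary in E3 3.e covers time of day, duration, "pain score prior to and after application, and presence of any pelvic floor symptoms prior to and after application".

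**The concern.** The protocol names discomfort with tube placement as a risk (E2 2.e), and names irritation, cold injury and vaginal trauma as theoretical adverse events (F3 3.a). It also says that outcomes of transvaginal cryotherapy have not been studied before (D1), and it calls the trial a pilot of efficacy and feasibility (G2). Tolerability is therefore one of the main things the trial can teach.

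A woman who finds the tube intolerable has more reason than most to withdraw, and withdrawal takes her out before the one point at which anyone asks about harm. An event she does not mention is neither graded nor tabulated, and it cannot count towards either pause rule.

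**Working it through.** The plan gives no figure on this point to reproduce: no expected withdrawal rate, intolerance rate or Class I rate. The check is a comparison of the sections, followed by the arithmetic of the pause rules.

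**Step 1. Routes by which an adverse event can reach the record, and what withdrawal does to each**

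- Adverse-event question at 2 weeks (F3 3.a): closed, because data collection has stopped and she is not contacted about later tasks.
- Diary (E3 3.e): none of the listed items is an adverse-event item, and entries end at withdrawal.
- Repeat examination within 10 minutes of the first in-office use (E3 3.b): this covers only that use in Aim 1, not the daily use at home.
- 24/7 contact (F3 3.a): open, but she must start it.
- The withdrawal call or letter (E2 2.f): she makes this contact, but the section lists no question about her reason or about adverse events.

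For a woman who withdraws during home use, only the last two routes remain, and both depend on her volunteering the event.

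**Step 2. Sensitivity of the pause rules to a missing report**

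For Class II or higher, one related event triggers a pause, so one unreported event is enough to miss it.

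For Class I, the smallest count that triggers with E patients enrolled is floor(0.10 × E) + 1. The values 20 and 33 for E are assumed; 66 is the planned total (F1, G1). Each line takes a true count exactly at the trigger and removes one report. The withdrawn patient still counts as enrolled.

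- E = 20: 0.10 × 20 = 2.0, so the trigger is 3 (3/20 = 15.0%). One missing leaves 2/20 = 10.0%, which is not more than 10%.
- E = 33: 0.10 × 33 = 3.3, so the trigger is 4 (4/33 = 12.1%). One missing leaves 3/33 = 9.1%.
- E = 66: 0.10 × 66 = 6.6, so the trigger is 7 (7/66 = 10.6%). One missing leaves 6/66 = 9.1%.

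If she were also dropped from the denominator, the shares would be 2/19 = 10.5%, 3/32 = 9.4% and 6/65 = 9.2%. The rule would then still fire at 20 enrolled, but not at 33 or 66.

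These lines show that one missing report can matter when the true count is at the threshold. They do not say how often that would happen.

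**Step 3. What an estimate would need**

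The expected number of missed events is the number enrolled × the share who withdraw × the share of those who had an event × the share of those who do not volunteer it. The documents give none of the last three terms, so the product cannot be calculated.

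**The case against.** The strongest reply is that the plan already has safeguards. A contact can be reached at all hours, reporting runs throughout, the first Aim 1 use is followed by an examination, and a woman must contact the team in order to withdraw, when she may well say why. A safety call after withdrawal is not expressly forbidden, since the no-contact wording covers study-related tasks. The data forms and consent document listed in section K are not reproduced, so a reason for leaving might be recorded there. F3 3.a also reports no adverse events in routine use. All of this stands, and it makes loss possible rather than certain. None of it, however, is an active question put to the woman who leaves.

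A reader might infer two stronger points, which the documents do not support.

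- **That a patient who stops using the tube is forced out of the study and lost from the 2-week outcome.** Section 2.f covers only a request to withdraw from the study. G4 plans an intention-to-treat analysis with a secondary per-protocol analysis, which presupposes that non-adherent patients remain in follow-up. What is missing is a sentence saying so. The exclusion of missing primary outcomes in G4 is a separate matter.
- **That withdrawal leads to destruction of the safety data.** The default is to keep and use them. Destruction needs a separate request from the patient, and honouring it is an ethics choice. Nothing says that a later deletion undoes a pause or review already triggered.

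**Conclusion.** The gap is real and narrow. As written, a woman who withdraws because of tube discomfort or injury is not actively asked about it at any point, and unless she volunteers it, her event is absent from the safety record and from both pause rules. The conclusion rests on the text of E2 2.f, E3 3.e and F3 3.a, and on the assumption that the forms we cannot see add no such question.

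Its size cannot be estimated from the documents. A reader might be tempted to set the 20% loss allowance in G1 against the 10% Class I trigger and conclude that the rule could be missed altogether. That does not follow. The 20% is an allowance for loss to follow-up and is not split into withdrawals and other losses. No share of it is tied to adverse events. The trigger for all 66 patients applies only when planned enrolment is complete, when there is nothing left to pause. The documents also do not say whether tube discomfort counts as a Class I complication, so the number of relevant events is unknown even in principle.

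This is a weakness in safety ascertainment that is worth closing because it is cheap to close. It does not invalidate the design.

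**What to change.** Amend E2 2.f in two places.

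1. When a withdrawal request is received, ask the patient once, voluntarily, for her reason and for any adverse event, and record the answer in REDCap before data collection stops. If she withdraws in writing, send one brief reply with the same question.
2. State that stopping use of the tube is not withdrawal from the study. Patients who only stop remain due for the 2-week examination, questionnaires and adverse-event question, in line with the intention-to-treat analysis.

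The cost is protocol and consent wording, one short question, and one extra message for a written withdrawal. The text should name who takes the answer: a reason such as the cold could reveal the arm to the blinded PI, and E2 2.d keeps the unblinded research assistant out of data collection.

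Whether a minimal de-identified adverse-event record survives a deletion request under 2.f and H3 is for the ethics board to decide. Both changes stand without it.
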